#### Concurrent Systemic Conditions

- Uncontrolled blood pressure (defined as systolic > 180 mmHg and/or diastolic > 110 mmHg while patient is sitting)  
If a patient's initial reading exceeds these values, a second reading may be taken 30 or more minutes later. If the patient's blood pressure needs to be controlled by antihypertensive medication, the patient can become

eligible if medication is taken continuously for at least 30 days prior to Day 0.

- Atrial fibrillation not managed by patient's primary care physician or cardiologist within 3 months of screening visit
- Women of childbearing potential not using adequate contraception (as defined in the inclusion criteria). A woman is considered not to be of childbearing potential if she is postmenopausal, defined by amenorrhea for at least 1 year in a woman > 45 years old; or has undergone hysterectomy and/or bilateral oophorectomy.
- History of stroke within the last 3 months of screening visit
- History of other disease, metabolic dysfunction, physical examination finding, or clinical laboratory finding giving reasonable suspicion of a disease or condition that contraindicates the use an investigational drug or that might affect interpretation of the results of the study or renders the patient at high risk for treatment complications
- Current treatment for active systemic infection
- Active malignancy
- History of allergy to fluorescein, not amenable to treatment
- Inability to obtain fundus photographs or fluorescein angiograms of sufficient quality to be analyzed and graded by the reading center
- Inability to comply with study or follow-up procedures
- Previous participation in any studies of investigational drugs within 1 month preceding Day 0 (excluding vitamins and minerals)

## **4.2 METHOD OF TREATMENT ASSIGNMENT**

Subjects will receive open-label IVT of 0.5 mg ranibizumab. Subjects will be randomized into a 1:2 ratio that will occur at Day 0.

- Cohort A – Subjects will receive monthly treatment of 0.5 mg IVT ranibizumab for 100 weeks. Starting at week 104 subjects will receive PRN IVT ranibizumab for another 56 weeks (total of 156 weeks)
- Cohort B – Subjects will receive 0.5mg IVT ranibizumab for 3 a minimum of consecutive visits (visit 2, 4 & 5) followed by a treat and extend protocol in which follow-up intervals are increased when there is no clinical and SD-OCT evidence of disease activity by 2-week intervals. Starting at week 104, if a subject has achieve the 12 week interval they will switch to monthly visits with PRN IVT ranibizumab through week 156. If a subject has not achieved a dry macula they will continue the treat and extend protocol until the 12 week interval is met and then switch to monthly visits with PRN IVT ranibizumab.

## **4.3 STUDY TREATMENT**

### **4.3.1 Formulation**

Ranibizumab is formulated as a sterile solution aseptically filled in a sterile, 3-mL stoppered glass vial. Each single-use vial is designed to deliver 0.05 mL

of 10-mg/mL ranibizumab aqueous solution with 10 mM histidine HCl, 10%,  $\alpha$ -trehalose dihydrate, and 0.01% polysorbate 20, pH 5.5. This results in the delivery of a 0.5 mg dose of ranibizumab. Each vial contains no preservative and is suitable for single use only.

Further details and molecule characterization are included in the Investigator Brochure.

#### **4.3.2 Dosage, Administration, and Storage**

##### **a. Dosage**

Patient will be to receive intravitreal injections of 0.5 mg of ranibizumab according to their specific cohort treatment schedule.

##### **b. Administration**

\*See Appendix B for detailed pre-injection procedures.

##### **c. Storage**

Upon receipt, study drug kits should be refrigerated at 2°C - 8°C (36°F - 46°F). DO NOT FREEZE. Do not use beyond the expiration date. Ranibizumab vials should remain refrigerated. Protect vials from direct light. Store in original carton until time of use.

RANIBIZUMAB VIALS ARE FOR SINGLE USE ONLY. Vials used for one subject may not be used for any other subject.

#### **4.4 CONCOMITANT AND EXCLUDED THERAPIES**

Subjects may continue to receive all medications and standard treatments administered for their systemic conditions at the discretion of their treating physician.

#### **4.5 STUDY ASSESSMENTS**

##### **4.5.1 Assessments during the Treatment Period**

\* Refer to Appendix A for a complete overview of study procedures

- Obtain informed consent prior to study procedures being performed at screening visit
- Obtain demographics
- Concomitant Medications reviewed at every visit
- Adverse Events reviewed at every visit

##### Vital Signs (All Study Visits)

- Vital signs will include measurements of pulse and systolic and diastolic blood pressure, while subject is in a seated position. Vital signs should be taken before injection of study drug.

### Ocular Assessments (All Study Visits)

- Best Corrected Visual Acuity Visual function of the study eye and the fellow eye will be assessed using the ETDRS protocol (The Early Treatment Diabetic Retinopathy Study Group, 1985) at 4 meters. (See Appendix F)
- IOP measurement of both eyes will be measured pre-dilation at every visit. IOP will be measured post intravitreal injection 30 min ( $\pm$  15 min) in the study eye. The method used for a subject must remain consistent throughout study.
- Slit lamp examination-Subject's anterior eye structure and ocular adnexa will be examined at each study visit using a slit lamp by the investigator.
- Indirect Ophthalmoscopy the subject's posterior pole and peripheral retina will be examined by indirect ophthalmoscopy at each study visit pre dose by the investigator
- Subjects will receive 0.5 mg intravitreal injection of ranibizumab per treatment schedule
- Telephone Safety Check 3 days ( $\pm$  1 day) post injection (after first injection only)

### Ocular Imaging

- Fundus Photography (FP) and Fluorescein Angiography (FA)- The anatomical state of the retinal vasculature of the study eye will be evaluated by fundoscopic examination, FP and FA. As well, as a measurement of the CNVM size performed at Screen, between weeks 24-28, 48-57, between weeks 72-82, between weeks 104, between weeks 124-128 and week 156.
- Optical Coherence Tomography (All Study Visits) – Ocular morphology will be evaluated using the Heidelberg Spectralis SD-OCT on the study eye. All SD-OCT images will be captured using the most current software. All SD-OCTs will be electronically archived at the site as part of the source documentation.
- Auto Fluorescence (AF) (All Study Visits) – Ocular morphology will be evaluated using the Heidelberg Spectralis on the study eye. All AF images will be captured using the most current software. All AF's will be electronically archived at the site as part of the source documentation

\*See Appendix E for Imaging Guidelines

### Other Testing (Performed at week 104, week 128 & week 156 or closest visit to each)

- Serum and/or plasma Samples

### Procedures performed at Endpoint Visits (if separate from a scheduled visit)

- Floating Endpoints (also known as the Biological Endpoints): ETDRS visual acuity, SD-OCT, AF, FP and FA
- Hard Endpoints: ETDRS visual acuity, SD-OCT and AF

#### **4.5.2 Early Termination Assessments**

Subjects who withdraw from the study prior to completion should return for an early termination evaluation 28 days ( $\pm$  7 days) following the last injection/study visit for monitoring of all adverse events (serious and nonserious). The schedule of assessments for early termination is the same as that for the final visit.

#### **4.6 SUBJECT DISCONTINUATION**

Subjects have a right to withdraw from the study at any time.

The subject may be withdrawn from the study for any reason: if it is in the best interest of the subject, intercurrent illness, adverse events, or worsening condition. The Retina Consultants of Houston or [name], MD, may request the withdrawal of a subject because of protocol violations, administrative reasons, or any other valid and ethical reasons.

If a subject discontinues from the study, he or she will not be allowed to re-enter the study.

Reasons for subject discontinuation may include, but are not limited to, the following:

- Sensory rhegmatogenous retinal detachment or Stage 3 or 4 macular hole
- Investigator determination that it is not in the best interest of the subject to continue participation
- Pregnancy
- Need for anti-VEGF therapy other than ranibizumab in the study eye, unless as a part of the prospective investigational study design
- SAE
- Any other safety concerns

In the event of an adverse event in the study eye that is considered by the investigator to be severe in intensity, serious consideration should be given to discontinuing the subject from the study.

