#### **3.2 OVERVIEW OF STUDY DESIGN**

This trial will compare the results of 2 cohorts, with different treatment intervals, to assess the safety, tolerability and efficacy of IVT of ranibizumab for the treatment of wet AMD. Specifically, this trial will evaluate the ability to reduce the amount of visits and IVT ranibizumab treatments needed all while maintaining an exudation-free macula. Subjects in both cohorts will be followed for a total of 156 weeks.

**Cohort A** (control arm, monthly, n=20) Subjects will receive monthly treatment of IVT 0.5 mg ranibizumab from Day 0 to week 100. Monthly treatment is defined as every 28 days (±7 days). Dosing should not occur earlier than 21 days after the previous treatment.

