#### **Monthly vs Extended Fixed Interval Schedules vs PRN Treatment**

Both MARINA and ANCHOR employed monthly ranibizumab dosing. While this treatment approach yielded exceptional results with sustained visual gains over 2 years, monthly doctor visits are often impractical and difficult for patients and their caregivers. Therefore, large prospective trials have evaluated 2 main alternative treatment approaches in an attempt to decrease the treatment burden while maintaining visual gains: fixed interval treatments with less than monthly dosing, and pro re nata (PRN) treatment.

Prior attempts at fixed interval schedules employing less than monthly treatments have resulted in disappointing visual outcomes. For example the PIER study, a phase IIIb, multicenter, randomized, controlled trial compared sham injections to ranibizumab monthly for 3 months and then quarterly. In stark contrast to the results of MARINA and ANCHOR, while visual outcomes were statistically better than the sham treated control group, the visual acuity improvement observed at month 3 was lost by month 12, with patients losing a mean of -1.6, and -0.2 letters in the 0.3 mg and 0.5 mg ranibizumab groups respectively. Similarly suboptimal outcomes were seen with the EXCITE and SAILOR results which employed similar quarterly dosing strategies without success.

Importantly, however, subgroup analysis of PIER patients who showed no recurrence of exudative disease activity after the first 3 months of treatment on quarterly dosing showed sustained visual gains compared to visual losses observed in patients who showed persistent exudative disease activity after the first 3 months of treatment (Brown D.M. et al RETINA. In press). It is likely that the prolonged and recurrent episodes of retinal edema observed in the majority of under-treated quarterly treated patients directly contributed to their poor visual outcomes. Therefore, it seems that while under-treatment of active exudative disease in the setting of wet AMD leads to suboptimal visual outcomes, not all patients require monthly dosing to achieve optimal visual outcomes; namely, those wet AMD patients without active exudative disease may be able to have a reduced treatment burden while maintaining their visual gains.

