## **4. MATERIALS AND METHODS**

### **4.1 SUBJECTS**

#### **4.1.1 Subject Selection**

60 subjects from approximately 4 sites in the United States will be enrolled. Eligible subjects who have provided informed consent will be screened for eligibility before the initiation of any study procedures. Screening evaluations may be performed at any time within the 14 days preceding Day 0. Subjects must have wet macular degeneration secondary to age, with no prior treatment; with disease activity seen on SD-OCT. Subjects can only have one eye in the study, if both eyes are eligible to be in the trial the investigator will determine which eye will be in the study (study eye). Genentech will supply drug for the non-study eye (fellow eye) if needed. Subjects will be randomized in a 1:2 ratio so that:

- 20 subjects will be randomized to the monthly arm (Cohort A)
- 40 subjects will be randomized to the TREX arm (Cohort B)

\*See Appendix A, the study flow chart, for screening assessments.

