#### **4.8.4 Missing Data**

Analyses of efficacy and safety will be based on available cases, without imputation for missing values.

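### Section 4.6 allows irreversible removal from the study for protocol violations or administrative reasons; with one exit visit and an available-case analysis, this can lose later acuity data non-randomly and bias the arm comparison

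*Combined protocol and SAP*

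**What the plan says.** Section 4.6 (Subject Discontinuation) first covers withdrawal in the subject's interest: best interest, intercurrent illness, adverse events, worsening condition. It then adds a separate power, under which the sponsor institution or a named physician "may request the withdrawal of a subject because of protocol violations, administrative reasons, or any other valid and ethical reasons". The removal is from the study and not only from the injections, and it is final: "If a subject discontinues from the study, he or she will not be allowed to re-enter the study".

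Section 4.2 states "Subjects will receive open-label IVT of 0.5 mg ranibizumab", so whoever asks for a withdrawal can know the arm. Section 4.5.2 asks a withdrawn subject to return once, 28 (±7) days after the last injection or study visit, for the final-visit assessments. The documents describe no later follow-up.

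On the analysis, Section 4.8.4 states: "Analyses of efficacy and safety will be based on available cases, without imputation for missing values". The primary measure (Section 4.8.3) is mean change in ETDRS acuity at six time points from about week 26 to week 156. Section 4.8.1 runs the analyses once each subject has completed the visit or discontinued early, and refers to a Statistical Analysis Plan for detail. The combined document contains no separate text of that plan. It defines neither an as-randomised analysis set nor what counts as a protocol violation serious enough for removal.

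**The concern.** Withdrawal for safety has a clinical reason. Withdrawal for a protocol violation or an administrative reason need not, and here it ends outcome collection as well as treatment. The two arms run on different schedules: 28-day visits in Cohort A, and individual intervals with step rules in Cohort B. The occasions for a violation can therefore differ by arm and, within Cohort B, with how the disease responds. If removals follow those occasions, the subjects seen at weeks 104 and 156 are no longer the groups that were randomised.

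This matters because the trial asks whether vision can be kept with fewer visits. Section 3.3 says that "monthly doctor visits are often impractical and difficult for patients and their caregivers", so difficulty in keeping to a schedule is part of what is being compared. Section 4.8.1 also allows week 52 and week 104 results by arm to be made public before the study ends, so the power to remove subjects continues after arm results may be known.

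**Working it through.** **1. What a removed subject loses.** Take, as an example, a last visit at week 56. The subject contributes to the time points near weeks 26 and 52. The early termination visit falls at week 56 + 4 = 60 (±1), outside every floating window (24-28, 48-57, 72-82, 104, 128-132, 156) and every hard endpoint (52, 104, 156). Four of the six primary time points are lost: weeks 72-82, 104, 128-132 and 156. With other exit dates the termination visit may fall inside one window, but it cannot supply the later ones.

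**2. Occasions for a timing violation, to the end of year 2.** Sections 3.2 and 2 give the schedules.

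- Cohort A, day 0 to week 100 every 4 weeks: 100/4 + 1 = 26 injections, 25 intervals.
- Cohort B, dry from week 8 and never recurring: weeks 0, 4, 8, 14, 22, 32, 44, 56, 68, 80, 92 = 11 injections, 10 intervals.
- Cohort B, never extended: 26 injections, 25 intervals, as in Cohort A.

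Both arms have the same ±7-day window. With an assumed chance p of missing the window at each interval, P(at least one) = 1 − (1 − p)^k, where k is the number of intervals:

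| Assumed p | Cohort A, or B never extended (k = 25) | Cohort B, fastest extension (k = 10) |
|---|---|---|
| 0.5% | 11.8% | 4.9% |
| 1% | 22.2% | 9.6% |
| 2% | 39.7% | 18.3% |

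Exposure can thus differ by arm and by disease response. The net direction is not fixed, because Cohort B also has extra endpoint visits and more complex interval rules. One of those rules is itself inconsistent. After three recurrences at an interval, Section 3.2 restarts extension in 1-week steps and the Cohort 2 notes in Appendix A in 2-week steps. These passages must be reconciled, since following one breaks the other.

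**3. Bias in the arm difference.** Section 4.1.1 gives 20 subjects in A and 40 in B, which is 60 split 1:2. Let w be the number removed from an arm, and g the letters by which removed subjects would have ended worse than those kept. An arm's mean over all randomised equals the mean of those kept minus g × w/n, so the observed arm mean is too high by g × w/n. With the same g in both arms:

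bias in (B − A) = g × (wB/40 − wA/20)

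One removal is 5% of A but 2.5% of B.

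| Removed from A | Removed from B | g = 5 | g = 10 | g = 15 |
|---|---|---|---|---|
| 2 | 0 | −0.5 | −1.0 | −1.5 |
| 4 | 0 | −1.0 | −2.0 | −3.0 |
| 0 | 4 | +0.5 | +1.0 | +1.5 |
| 2 | 4 | 0 | 0 | 0 |

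If removed subjects would have done better (g negative), every sign reverses.

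**4. Scale.** The documents give no SD. For an assumed SD of 10 to 15 letters, SE = SD × √(1/20 + 1/40) = 2.74 to 4.11, and the 95% half-width is 1.96 × SE = 5.4 to 8.1 letters. The biases in step 3 are smaller than this sampling error. Unlike it, they are systematic and the analysis would not show them.

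**The case against.** The strongest reply is that the clause is permissive, leaves protocol violations undefined, and is one of several routes out of the study. The reasons listed in Section 4.6 name no missed or late visit. The entry criteria select subjects able and willing to attend, which argues for few such removals. All of this stands, and it rules out several stronger readings that a reader might infer:

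- *That adherence to the schedule decides who remains.* The text says only that withdrawal may be requested. Adherence can affect who remains; nothing shows that it will.
- *That only completers are analysed.* An available-case rule keeps a withdrawn subject at every time point already reached, and possibly at the termination visit. The loss is of later time points.
- *That monthly dosing, or treat-and-extend, is made to look better.* This needs removed subjects to do worse, and more of them to go from one arm. The documents show neither. A Cohort B interval set wrongly may be a site error, and a subject treated too often could do better.
- *That the overstatement of one arm's mean is the bias of the comparison.* It is not: equal fractions with equal g cancel.

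The missing Statistical Analysis Plan text may contain an as-randomised or sensitivity analysis. That could soften the problem, but it cannot supply acuity that was never measured.

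**Conclusion.** The point holds in a limited form. Sections 4.6, 4.5.2 and 4.8.4 together permit irreversible removals unrelated to safety, in an open-label trial, with at most one later acuity measurement. Such removals can cause non-random loss at later time points and can bias the arm difference if they differ by arm or by outcome. The direction is unknown. With two removed from A and none from B the bias is −0.5 to −1.5 letters; with four from A and none from B it is −1.0 to −3.0; with equal fractions and equal g it is 0. The numbers removed, g, p and the SD are all assumptions, and no sample-size figure in the plan depends on this point. It is a cheap improvement, not a flaw that invalidates the comparison.

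**What to change.** Amend Section 4.6 so that protocol violations and administrative reasons are recorded as deviations and are not grounds for removing a subject from the study. State that the catch-all wording does not readmit them; deleting the two named grounds alone would leave both the closing catch-all and the general opening phrase of that paragraph available. Leave the safety and best-interest grounds as they are.

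Separate stopping study injections, which stays with the investigator, from leaving the study. Unless the subject withdraws consent, continue the scheduled BCVA, SD-OCT and adverse event assessments through weeks 52, 104 and 156. Section 5.2.1 needs a matching edit, because adverse event reporting now ends 30 days after the last study treatment or study discontinuation, whichever is earlier. In Section 4.8, analyse subjects in the arm to which they were randomised, and report withdrawals by arm and reason.

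The cost is a wording change, continued visits for a few subjects, and some off-schedule data to describe.

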#### **4.7 STUDY DISCONTINUATION**

Retina Consultants of Houston or Genentech may terminate this study at any time. Reasons for terminating the study may include the following:

- The incidence or severity of adverse events in this or other studies indicates a potential health hazard to subjects
- Subject enrollment is unsatisfactory
- Data recording is inaccurate or incomplete

#### **4.8 STATISTICAL METHODS**

##### **4.8.1 Analysis of the Conduct of the Study**

The analysis of data from week 52, week 104 and week 156 treatment period will be performed when all subjects have either completed the visit at week 52, week 104 and week 156 or discontinued early from the study.

The analysis of complete data (week 156) for the study will be performed when all subjects have either completed the visit at week 156 or discontinued early from the study, all data collected from the study are in the database, and the database is locked. Aggregate results of the week 52, week 104 and week 156 analysis, summarized by treatment group, may be reported to the public before completion of the study.

Descriptive summaries will include the mean, standard deviation, median, and range for continuous variables, counts and percentages for categorical variables.

Unless otherwise specified, all statistical tests are two sided. Detailed specifications of the statistical methods are described in the Statistical Analysis Plan.

#### **4.8.2 Safety Analyses**

Any adverse events, laboratory assessments, physical examinations, vital signs, ocular examinations and measurements from all 60 subjects will be utilized to summarize safety data for this study.

#### **4.8.3 Efficacy Analyses**

##### **Primary Outcome Measure**

The primary outcome measure for safety, tolerability and efficacy are:

- Mean change in ETDRS visual acuity from baseline to weeks 24-28, baseline to weeks 48-56, baseline to weeks 72-82, baseline to week 104, baseline to weeks 128-132 and baseline to week 156.

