### **3. STUDY DESIGN**

#### **3.1 DESCRIPTION OF STUDY**

TREX is a phase IIIb, multicenter, randomized, controlled clinical study. Subjects will be randomized 1:2 to “monthly” (control arm) or “treat and extend” protocol (comparator arm) respectively. TREX assess the safety, tolerability and efficacy of intravitreal injections (IVT) of 0.5mg ranibizumab given monthly for up to 100 weeks followed by pro re nata (PRN) treatment for 56 weeks compared to a Treat and Extend protocol for 156 weeks in patients with wet age-related macular degeneration (AMD). Subjects treated in a treat and extend protocol receive 3 consecutive IVT 0.5 mg ranibizumab (visits 2, 4 and 5). Starting at week 8, if a subject has achieved a “dry” macula; signs of active exudation have resolved will begin a Treat and Extend protocol (visits lengthened by 2 week intervals every visit a dry macular is maintained). At the beginning of the 104-week endpoint subjects initially randomized to the TREX cohort will transition to PRN re-treatment when there is no exudative disease activity at the 12-week interval.

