##### **Secondary Outcome Measures**

- Incidence and severity of adverse events (ocular and non-ocular).
- Total number of intravitreal injections required from baseline through weeks 48-57 (week closest to week 52), baseline through week 104 and baseline through week 156.
- Total number of office visits and imaging studies performed from baseline through weeks 24-28 (week closest to week 26), baseline through weeks 48-56 (week closest to week 52), baseline through weeks 72-82 (week closest to week 78), baseline through week 104, baseline through weeks 128-132 (week closest to week 132) and baseline through week 156.
- Percentage of subjects with persistent active exudation on SD-OCT from baseline through weeks 48-57 (week closest to week 52), baseline through week 104 and baseline through week 156.

- Percentage of subjects with persistent leakage on fluorescein angiography from baseline through weeks 24-28, baseline to weeks 48-56, baseline to weeks 72-82, baseline to week 104, baseline to weeks 128-132 and baseline to week 156.
- CNVM lesion size at baseline, compared to baseline to weeks 24-28, baseline to weeks 48-56, baseline to weeks 72-82, baseline to week 104, baseline to weeks 128-132 and baseline to week 156, as determined by fluorescein angiography.
- Mean change in central foveal thickness by SD-OCT from baseline to weeks 48-57, baseline to week 104 and baseline to week 156.
- Mean change in BCVA by ETDRS letter score from baseline through weeks 24-28, baseline through weeks 48-56, baseline through weeks 72-82, baseline to week 104, baseline through weeks 128-132 and baseline to week 156.

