### **Endpoint Visits:**

Few completed prospective trials have employed a treat and extend protocol. Therefore, there is little data regarding optimal endpoint usage. These endpoints will allow comparison of data from each cohort.

1. **Floating Endpoints** (also known as the Biological Endpoints): Analyses will be performed between weeks 24-28, between weeks 48-57, between weeks 72-82, week 104, between weeks 128-132 and week 156 (range to be determined by timing of last injection). If more than one possible endpoint exists, the time point closest to week 26, week 52, week 78, week 104, week 130 or week 156 will be used. This will be applied to both Cohort A and B, but likely to be most important for Cohort B. All endpoints are measured 4 weeks following the last injection.
2. **Hard Endpoints:** analyses will be performed at week 52 (day 365 $\pm$  7 days), week 104 (day 730  $\pm$  7 days) and week 156 (day 1095)

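### Visual-acuity change is primary at six unranked time points and repeated as secondary; name one baseline-adjusted week-104 contrast, state that it is the floating value, and give it a numeric window.

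*Combined protocol and SAP*

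**What the plan says.** **Primary.** Sections 2.1, 3.4.1 and 4.8.3 give the primary measure as "Mean change in ETDRS visual acuity from baseline to weeks 24-28, baseline to weeks 48-56, baseline to weeks 72-82, baseline to week 104", followed by weeks 128-132 and week 156. No order or lead time point is given.

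**Secondary.** Sections 2.2, 3.4.2 and 4.8.3 also list "Mean change in BCVA by ETDRS letter score from baseline through weeks 24-28", continuing through the same six times.

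**Endpoint types.** The Endpoint Visits text in 4.8.3 defines a floating series at six times ("All endpoints are measured 4 weeks following the last injection") and a hard series at weeks 52, 104 and 156. The floating list carries the note "range to be determined by timing of last injection". Its week-52 window is 48-57, against 48-56 in the primary list. Week 104 is in both series, and the floating version has no numeric window.

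**Analysis.** Section 4.8.1 schedules analyses at weeks 52, 104 and 156, describes descriptive summaries, and says "Unless otherwise specified, all statistical tests are two sided". It then says "Detailed specifications of the statistical methods are described in the Statistical Analysis Plan". Section 4.8.4 says "Analyses of efficacy and safety will be based on available cases, without imputation for missing values". The supplied text states no alpha, hypothesis, between-arm contrast, model or covariate.

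**Regimens.** Section 3.1 describes monthly treatment "followed by pro re nata (PRN) treatment for 56 weeks compared to a Treat and Extend protocol for 156 weeks". Under sections 3.2 and 4.2, all of Cohort A moves to PRN at week 104. Cohort B subjects move only once dry at the 12-week interval.

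**The concern.** With six primary results and no lead, a reader cannot tell in advance which one the trial will be judged on. Section 4.8.1 allows aggregate results from weeks 52, 104 and 156 to be made public before the study is complete, so the main time point could be settled after some results are known. Listing one measure as both primary and secondary removes the distinction between the two.

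Week 104 has a second ambiguity. In Cohort A the last monthly injection is at week 100, so the floating and hard values coincide. In Cohort B they need not, so the choice changes the time since injection in one arm only.

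The six points also do not all answer the same question. After week 104 the arms no longer compare monthly dosing with treat-and-extend, because all of Cohort A and only part of Cohort B have moved to PRN. Those later times serve the year-3 aims in section 3.3.

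Finally, with 20 against 40 subjects, an unadjusted change score carries part of any chance baseline imbalance into the contrast.

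**Working it through.** **No planned figure to reproduce.** Section 4.1.1 gives 60 subjects, 20 and 40, without power, SD, effect size or margin. Alpha, SDs and correlations below are assumptions.

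**1. Floating against hard at week 104, Cohort B.** Inputs are from section 3.2 and Appendix A: injections at weeks 0, 4 and 8; a 4-week interval until dry; then 2 weeks longer at each dry visit, up to 12 weeks. Floating value = injection week + 4, taking the value closest to week 104. Weeks are nominal.

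| First dry, then always dry | Later injections | Floating value nearest week 104 | Weeks since injection at hard week 104 |
|---|---|---|---|
| Week 8 | 14, 22, 32, 44, 56, 68, 80, 92 | 96; or 108 if injected at week 104 | 12 |
| Week 12 | 12, 18, 26, 36, 48, 60, 72, 84, 96 | 100 | 8 |
| Week 16 | 12, 16, 22, 30, 40, 52, 64, 76, 88, 100 | 104 | 4 |

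In the first row, a week-104 injection adds a value at week 108. That is 4 weeks from the target against 8 for week 96, so the closest-value rule picks 108. The documents do not agree on whether that injection is given. Section 2 has injections at every scheduled visit only to week 103. Section 3.2 withholds treatment at the visit where the 12-week interval is achieved during weeks 104-156. The Cohort B footnote in Appendix A exempts only week 156.

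**2. Multiplicity.** Equally correlated normal test statistics, each tested two-sided at an assumed 0.05 (|z| > 1.96), 1,000,000 simulated draws. Chance of at least one false positive:

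| Correlation | Six time points | Three scheduled analyses |
|---|---|---|
| 0.5 | 20.8% | 12.5% |
| 0.7 | 16.4% | 10.9% |
| 0.9 | 10.9% | 8.3% |

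**3. Precision of one contrast.** Half-width = t × SD × sqrt(1/20 + 1/40), with t on 58 degrees of freedom = 2.002 and sqrt(0.075) = 0.2739.

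- SD of change 10: 2.002 × 10 × 0.2739 = 5.48 letters.
- SD of change 15: 2.002 × 15 × 0.2739 = 8.22 letters.

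**4. Effect of baseline adjustment.** Let k be final SD divided by baseline SD, and ρ the baseline-final correlation. The ratio of adjusted variance to change-score variance is k²(1 − ρ²) / (1 + k² − 2kρ). For k = 1 this is (1 + ρ)/2.

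| k | ρ | Variance ratio | Half-width, SD of change 10 |
|---|---|---|---|
| 1 | 0.3 | 0.65 | 5.48 × sqrt(0.65) = 4.42 |
| 1 | 0.7 | 0.85 | 5.48 × sqrt(0.85) = 5.05 |
| 1.3 | 0.3 | 1.5379/1.91 = 0.805 | 4.92 |
| 1.3 | 0.7 | 0.8619/0.87 = 0.991 | 5.46 |

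The share of a chance baseline difference carried into a change score is 1 − kρ: 70% to 30% for k = 1, and 61% to 9% for k = 1.3. The case k = 1.3 matters because section 4.1.2 restricts baseline acuity to 20/32-20/400, while final acuity is unrestricted. This is a single-visit approximation that ignores the one degree of freedom spent on baseline.

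**The case against.** **The SAP may settle it.** Section 4.8.1 points to an SAP that is not in the supplied file. A reader might infer that no model, contrast or multiplicity rule exists. The documents do not support that; they show only that none is in the supplied text. The fix is therefore conditional. The unranked list and the duplicate are in the protocol itself and stand.

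**The endpoint type is not wholly open.** The six primary points match the floating list apart from 48-56 against 48-57. Three of them (weeks 24-28, 72-82 and 128-132) have no hard counterpart, and floating visits have a selection rule: 4 weeks after injection, closest to the target week. So floating is the natural reading. What remains is that the primary definition does not say it and that week 104 has no numeric window.

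**Multiplicity is hypothetical.** A reader might infer that the trial's error rate is inflated to 21%. No alpha, hypothesis or test of all six is stated, and analyses are scheduled at only three times. The percentages apply only if those tests are run.

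**Available cases need not mean biased means.** A reader might infer that section 4.8.4 prescribes separate means at each visit and that dropout biases them. It does not say how values are combined, and a likelihood-based repeated-measures model also uses available values without imputation. Any gain against dropout bias needs outcome-related loss that differs by arm, and the documents give no dropout rates. In a simulation with assumed loss of 10% in Cohort A and 22% in Cohort B, available-case bias was 0.76 letters against a standard error of 2.86 (0.27 SE). With equal 10% loss there was essentially none. The case for the model therefore does not rest on dropout.

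**Week 104 is a reviewer's choice.** True. It is supported by being the last planned time point before Cohort A moves to PRN.

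**Conclusion.** The concern holds in a limited form. The protocol makes one measure primary at six unranked times and secondary at the same six, and uses two different week-52 windows. It does not state that the primary series is floating, and it leaves floating week 104 without a numeric window, although in Cohort B that value can lie from week 96 to week 108 on the schedules worked above.

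The size depends on assumptions. If tested at 0.05 with correlation 0.9 to 0.5, six points give an 11% to 21% chance of at least one false positive, and three give 8% to 12.5%. With an SD of change of 10 and ρ of 0.3 to 0.7, adjustment cuts the half-width from 5.5 letters to 4.4-5.1 if variances are equal, but only to about 4.9-5.5 if the final SD is 1.3 times baseline. The gain in precision therefore ranges from useful to negligible. The firmer gain is that the main result is fixed in advance. This should be changed, but nothing here shows that the trial's comparison is invalid.

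**What to change.** Unless the SAP already fixes these points (if so, copy them into 4.8.3):

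1. Name one lead estimate: Cohort B minus Cohort A change in BCVA from baseline to week 104, with a 95% CI, framed as estimation.
2. State that it is the floating value, and report the hard week-104 value as supportive.
3. Give floating week 104 a numeric window wide enough for the 4-week post-injection values that the schedule produces, for example nominal weeks 96-108. Say how the ±7-day visit allowance applies.
4. Reconcile section 2, section 3.2 and the Appendix A footnote on whether a week-104 injection is given in Cohort B. Which rule applies is for the sponsor.
5. Make the earlier time points supportive, and report weeks 128-132 and 156 as year-3 strategy outcomes.
6. Delete the duplicate BCVA item from the secondary lists (2.2, 3.4.2, 4.8.3), and use one week-52 window throughout.
7. Estimate the lead contrast with a repeated-measures model adjusted for baseline BCVA, fitted to the floating windows up to week 104. Analyse the hard week-104 value by ANCOVA with baseline BCVA, so that the two endpoint types are not mixed in one model. Covariance structure, degrees-of-freedom method and any delta values for sensitivity analysis are the sponsor's choice.

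**Cost.** These are wording changes; section 4.5.1 already collects BCVA at every visit and at both endpoint types. One time point will carry the main conclusion, and at 20 against 40 the interval stays wide. The floating value equalises time since injection, but can fall several weeks away from week 104.
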